7.6 Known AEs List

Tildrakizumab

Tildrakizumab side effects include:

- Nasopharyngitis
- Diarrhea
- Injection site reaction

Tacrolimus

Tacrolimus side effects include:

- Neurologic: confusion, dizziness, insomnia, seizures, tremors, changes in how clearly one can think
- Cardiovascular: hypertension
- Gastrointestinal: nausea, vomiting
- Hematologic: microangiopathic hemolytic anemia, thrombocytopenia
- Endocrine and metabolic: hypomagnesemia, hypokalemia, hyporalcemia, hyperlipidemia
- Miscellaneous: unwanted hair growth, changes in vision, liver problems, reversible renal insufficiency, infections and posttransplant lymphoproliferative disorders

Methotrexate

The most frequently reported adverse reactions associated with methotrexate use as GVHD prophylaxis include:

- Neurologic: fever, dizziness, chills, undue fatigue
- Gastrointestinal: ulcerative stomatitis, nausea, abdominal distress, diarrhea
- Hematologic: leucopenia, anemia and suppressed hematopoiesis (leading to infection)

Miscellaneous

Abnormal liver tests, kidney failure and pulmonary complications after transplantation

8 PHARMACEUTICAL INFORMATION

Tildrakizumab

- **8.1 Agent Description:** Tildrakizumab is a high affinity (297 pM), humanized immunoglobulin G1/kappa ($IgG1/\kappa$) antibody that specifically binds and neutralizes human IL-23 (SN 08197 [Addendum 1]). This antibody has been shown in Phase 1, Phase 2, and Phase 3 studies to reduce the clinical signs and symptoms of psoriasis.
- **8.2 Absorption:** Absolute bioavailability is 73–80% with slow absorption with time to reach maximum concentration at 6.2 days after SC injection. Tildrakizumab exposure increased

proportionally with dose and did not exhibit time-dependent PK. Steady-state is achieved by 16 weeks with the clinical regimen (dosing on Week 0 and Week 4 and Q12W thereafter) with 1.1fold accumulation in C_{max} . Tildrakizumab has low to moderate PK variability (33-41% CV).

- 8.3 Distribution: Tildrakizumab has limited extravascular distribution with an apparent volume of distribution (Vd/F) of 10.8 L, which was found to depend on the body weight. Plasma protein binding is not expected to impact tildrakizumab exposure.
- **8.4 Metabolism:** Tildrakizumab is catabolized by general protein degradation processes; typical small-molecule metabolic pathways (e.g., CYPs), glucuronosyltransferases) do not contribute to its clearance.
- **8.5 Elimination:** Tildrakizumab is catabolized into component amino acids by general protein degradation processes and is not eliminated by renal or hepatic pathways. Apparent clearance is independent of dose. Apparent elimination half-life (%CV) is 23.4 days (23%).
- **8.6 Contraindications:** As tildrakizumab is eliminated by protein catabolism, not affected by hepatic drug metabolizing enzymes and not eliminated by renal or hepatic pathways, no dose adjustments for tildrakizumab are necessary when co-administered with other therapies.
- 8.7 Side Effects: Complete and updated adverse event information is available in the Investigational Drug Brochure and/or product package insert.
- 8.8 Storage Requirements and Stability: Ongoing stability studies have shown that tildrakizumab solution DP in PFS is stable under refrigerated storage conditions (2°C to 8°C). Please refer to the package insert for additional storage and stability information.
- 8.9 Agent Destruction and Return: Used, and any unused study drug will be destroyed and documented, as per institutional standards.

8.10 Availability

This drug is commercially available for the indication of psoriasis. For the purpose of this study, it will be paid for and supplied by the funding sponsor, Sun Pharmaceutical Industries Ltd. For drug ordering, fill out the drug supply form request form provided by Sun Pharmaceutical Industries Ltd.

9 CORRELATIVE STUDIES/SPECIAL STUDIES

9.1 DESCRIPTION

We intend to perform correlative studies to understand the impact of anti-IL-23 antibody treatment post allogeneic hematopoietic progenitor cell transplantation. This testing should help us better understand the changes that are happening within the immune system to inhibit graft-versus-host disease (GVHD).

We plan to perform the analysis of immune cells subsets from fresh or frozen peripheral blood mononuclear cells by flow cytometry, with the hypothesis that treatment with anti-IL-23 antibody will prevent alterations in circulating immune cell subsets and cytokines/biomarkers that are associated with development of GVHD.

MCW Protocol No: PRO00035737 43 Version No. 7 Version Date: 10/31/2022

Analysis of immune cell subsets from fresh or frozen peripheral blood mononuclear cells (PBMCs) by flow cytometry

As a measure of systemic immunity (using PBMCs), the relative percentage of circulating immune cells will be assessed by multiparametric flow cytometry. Multiparametric flow cytometry will allow for identification of immune cell subsets by recording the simultaneous expression of biomarkers unique to that cell subset. Flow cytometry will be performed on a MACS Quant flow cytometer in the Cell Therapy Laboratory at the Medical College of Wisconsin. We will use flow cytometry of antibody stained PBMCs to evaluate the relative percentage of cell types including T, B, NK and myeloid cells. Correlating changes in immune cell subsets upon anti-IL-23 therapy will facilitate the identification of a peripheral immune signature that correlates with absence or presence of GVHD. We will test for the expression of the following immune cell markers: T cell marker panel (includes regulatory T cell markers): CD3, CD4, CD8, CD25, CD44, CD62L, CD56, CD127, Foxp3 (intracellular), phospho-STAT3 (intracellular); NK cell marker panel: CD56, CD16, CD3; Myeloid cell marker panel: CD11b, CD33, CD14; B cell marker panel: CD19, CD20.

We also intend to perform the analysis of cytokines and biomarkers in blood plasma. Plasma, or serum, cytokine and biomarker signatures can provide important information regarding peripheral immune responses. Changes in serum cytokines and other biomarkers have been reported during GVHD and in cancer patients. However, currently, there are no defined cytokine signatures that are predictive of outcome following allogeneic hematopoietic progenitor cell transplantation.

Analysis of cytokines and biomarkers in blood plasma (Luminex[®] platform)

For this study, plasma cytokines and other biomarkers will be analyzed longitudinally before and after immune therapy with anti-IL-23 antibody. Serum cytokines will be quantified using customized Luminex[®] bioplex assays. For the **cytokine array**, we will analyze the following: IL-1, IL-2, IL-4, IL-6, IL-10, IL-17, IL-23, TNFα, GM-CSF, IFNγ. The biomarker array will analyze the following: ST2, REG3A, BAFF, CCL15, MMP3, CXCL9, CXCL10, osteopontin, soluble CD163.

9.2 Instructions Regarding Sample Collection for Correlatives:

For each time point, one 10 ml red top tube and one 10 ml purple top tube will be collected. Once the samples are collected, study coordinator will contact the BMT and Cell Therapy Laboratory [contact]).

The samples will be transferred to [name] lab once collected (no spinning or other special handling). They can be at room temperature. If they were to be collected on weekends or holidays, the samples should be stored at 4°C until they are transferred to the lab.

10 STATISTICAL CONSIDERATIONS

10.1 Study Endpoints

The endpoints are defined with more detail in Sections 2.3 through 2.5.

Primary endpoint

The primary endpoint is the 12-month probability of GVHD-free relapse-free survival (GRFS). An event for this outcome is defined as either grade III-IV acute GVHD, systemic therapy-requiring chronic GVHD, relapse, or death at 12 months.

MCW Protocol No: PRO00035737 44 Version No. 7 Version Date: 10/31/2022

Secondary endpoints

- 1. Cumulative incidence of mild, moderate and severe chronic GVHD according to the NIH criteria and limited or extensive GVHD by conventional criteria.
- 2. Cumulative incidence of grade II–IV acute GVHD at days 100 and 180.
- 3. Cumulative incidence of grade III–IV acute GVHD at days 100 and 180.
- 4. Incidence of primary and secondary graft failure.
- 5. Hematopoietic recovery will be assessed according to neutrophil and platelet counts recovery after HSCT.
- 6. Cumulative incidence of non-relapse mortality (NRM) post HSCT.
- 7. Cumulative incidence of relapse/progression of the primary malignancy.
- 8. Overall survival (OS) post HSCT.
- 9. Assess the pharmacokinetic (PK) profile of multi-dose tildrakizumab.
- 10. Probability of lower GI tract GVHD.

Exploratory endpoints

- 1. Longitudinal trajectory of serum cytokines.
- 2. Longitudinal trajectory of serum biomarkers.
- 3. Longitudinal trajectory of immune cell markers.

10.2 Study Design

10.2.1 Determination of Sample Size and Accrual Rate

[name] will assist with the statistical analyses in the trial. The study will test the primary hypothesis that GRFS at 12 months exceeds the historical control value of 20% at a two-sided 10% significance level. The target sample size will be 55 patients with a known outcome (i.e., GVHD, relapse, or death status at 12 months). With this sample size the study will have 80% power to detect an increase in GRFS at 12 months to 35%, 94% power to detect an increase to 40%, and 54% power to detect an increase to 30%. Justification for the 15% increase in GRFS probability as a clinically meaningful endpoint derives from the recently published BMT Clinical Trials Network 1203 GVHD prevention trial which compared three different prophylaxis regimens to standard therapy with tacrolimus and methotrexate and was powered to detect a 15% increase in GRFS. To achieve the target sample size, we will enroll 55 patients to allow for a 10% loss to follow-up.

10.2.2 Accrual Estimates

It is estimated that 30 months of accrual will be adequate. This is based on our historical rate of approximately 50 myeloablative allogeneic stem cell transplants per year over the past three years. Assuming a conservative 40% enrollment rate, approximately 30 months should be sufficient to enroll our target of 55 patients.

10.3 Analysis Population

The **full analysis set** will include all patients enrolled in the study.

The **efficacy analysis set** will include all patients in the full analysis set who receive at least one dose of tildrakizumab.

MCW Protocol No: PRO00035737 45 Version No. 7
Version Date: 10/31/2022

The biomarker analysis set will include all patients in the efficacy analysis set who have at least one evaluable biomarker sample.

10.3.1 Primary Analysis (or Analysis of Primary Endpoints)

The primary endpoint will be evaluated in the efficacy analysis set. The GRFS will be estimated using the Kaplan-Meier estimator and plotted with a 90% confidence band. An event for this outcome is defined as grade III-IV acute GVHD, chronic GVHD requiring systemic therapy, relapse or death. Patients who are alive without GVHD or relapse will be censored at the last follow-up. The 12-month GRFS will be compared to the prespecified historical control value of 20% using a one-sided z-test at a 5% significance level.

10.3.2 Secondary Analysis (or Analysis of Secondary Endpoints)

The secondary endpoints will be evaluated in the efficacy analysis set. Time-to-event outcomes with and without competing risks will be analyzed using Kaplan-Meier and Nelson-Aalen estimates, respectively, and presented with 95% confidence intervals. Binary outcomes will be analyzed using proportions and presented with 95% confidence intervals.

Bacterial community composition will be characterized using OTU counts generated as described above. OTU counts will be converted to measures of relative abundance to account for variation in sequencing coverage between samples. Statistical analysis will be carried out using the statistical software package R (www.r-project.org). Alpha (α) diversity (richness and evenness of taxa within a population) will be reported using the Shannon Index⁴⁶ and Chao1 richness estimator. ⁴⁷ Beta (β) diversity (overlap in taxa shared between populations) will be analyzed using the Bray-Curtis dissimilarity metric⁴⁸ in conjunction with multivariate statistical analysis methods that will include Principal Components Analysis (PCA) and Permutational Multivariate Analysis of Variance (PERMANOVA).⁴⁹ Changes in abundance of individual taxa will also be analyzed using traditional univariate statistical methods.

10.3.3 Other Analyses/Assessments

Demographic and other baseline data, such as disease characteristics, as well as outcome measures, will be presented for the full analysis set overall and separately for unrelated and matched related donor patients. Categorical data, such as gender, race, etc. will be presented by frequencies and percentages. Descriptive summary statistics (e.g., frequency, mean, median, range and standard deviation) will be used to present numeric data.

10.4 Evaluation of Safety

Analyses will be performed for all patients having received at least one dose of study drug. The study will use the NCI CTCAE v5. The frequency and proportion of patients experiencing an SAE will be reported with 95% confidence intervals overall, as well as classified by grade and organ system.

10.5 Stopping Rules

Formal statistical monitoring will be in place for 100-day overall mortality and 100-day grade 3-4 aGVHD rate. Based on program experience, a 100-day mortality rate <10% and a 100-day aGVHD rate of <15% are expected in the study population. Using a Bayesian approach to

MCW Protocol No: PRO00035737 Version No. 7 46

toxicity monitoring as implemented by J. Jack Lee, Ying-Wei Kuo, Diane Liu and Nan Chen (http://www.trialdesign.org/one-page-shell.html#BTOX), we derived a stopping boundary that pauses the trial if we are 90% confident that the probability of the monitored event exceeds the historical value, i.e., 100-day mortality exceeds 10% or 100-day grade 3–4 aGVHD rate exceeds 15%. A Beta prior distribution with effective sample size of 1 and mean equal to the historical value was used with a maximum of 37 patients, and a continuous evaluation starting at two patients. The following tables show the number of 100-day mortality and grade 3–4 aGVHD events that would trigger a safety review depending on the number of evaluable patients. For the purposes of the safety monitoring patients in the safety set who are alive with at least 100 days of follow-up or have experienced the monitored event within 100 days are considered evaluable.

Number of Evaluable	Boundary for excessive
Patients	100-day mortality
1	-
2–6	2+
7–12	3+
13–18	4+
19–25	5+
26–33	6+
34–37	7+
41–48	8+
49–54	9+

Number of Evaluable	Boundary for excessive
Patients	grade 3–4 aGVHD
1	-
2–4	2+
5–8	3+
9–13	4+
14–17	5+
18–22	6+
23–27	7+
28–33	8+
34–37	9+
39–43	10+

44–49	11+
50–54	12+

The following table shows the probability of finding excessive 100-day mortality and 100-day grade 3–4 aGVHD rate during the study for several underlying true values of the outcomes.

Underlying 100-day event rate	Probability of crossing mortality boundary	Probability of crossing aGVHD boundary
5%	4.8%	1.9%
10%	24%	9.8%
15%%	53%	28%
20%	78%	53%
25%	92%	76%
30%	98%	90%

If a stopping rule is triggered based on excessive 100-day mortality or 100-day grade III–IV aGVHD, the trial will be paused. The DSMC will meet and review all relevant data. They will determine the relevant next steps in terms of permanent discontinuation of the trial versus additional safety modifications needed to allow the trial to continue.

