3.2 Treatment Schema

Patients enrolled on this clinical trial will receive tacrolimus initiating at day -3 at doses to maintain therapeutic levels per institutional preference and continued until at least day +90 post-transplant. Methotrexate will be administered intravenously and dosed at 15 mg/m² days +1, and 10 mg/mg² on days +3, +6 and +11. Tildrakizumab will be administered subcutaneously at a dose of 100 mg on day -1, day 28±3, day 112±7, day 196±14, and day 280±14.

Number of patients who will be enrolled in the study: 55.

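### The safety stopping rule was evaluated for 37 patients but the trial enrols 55: the crossing probabilities are up to 10 points too low, and no boundary is given at 38–40 (mortality), 38 (aGVHD) or 55 (both)

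*Combined protocol and SAP*

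**What the plan says.** Section 10.5 (Stopping Rules) sets formal monitoring of 100-day mortality against a historical 10% and of 100-day grade 3–4 aGVHD against a historical 15%. The rule "pauses the trial if we are 90% confident that the probability of the monitored event exceeds the historical value". The prior is described as "A Beta prior distribution with effective sample size of 1 and mean equal to the historical value", and it "was used with a maximum of 37 patients, and a continuous evaluation starting at two patients".

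Two boundary tables follow. The mortality table goes from 34–37 (7+) directly to 41–48 (8+) and ends at 49–54 (9+). The aGVHD table goes from 34–37 (9+) directly to 39–43 (10+) and ends at 50–54 (12+).

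A third table is introduced as giving the "probability of finding excessive 100-day mortality and 100-day grade 3–4 aGVHD rate during the study". At true rates of 5, 10, 15, 20, 25 and 30% it states 4.8, 24, 53, 78, 92 and 98% for mortality, and 1.9, 9.8, 28, 53, 76 and 90% for aGVHD.

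The planned enrolment is 55. Section 3.2 states "Number of patients who will be enrolled in the study: 55", and section 10.2.1 states "we will enroll 55 patients to allow for a 10% loss to follow-up".

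**The concern.** The rule is described for 37 patients in a trial of 55, and nothing in the protocol limits monitoring to the first 37. The boundary rows beyond 37 show that monitoring is meant to continue. The breaks at 37 in both tables suggest that a 37-patient version was extended without completing its last row or recalculating the probabilities. That history is an inference; the mismatch itself is on the page.

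There are two consequences. First, the DSMC and IRB, who approve the monitoring plan (section 11), judge it on crossing probabilities that do not belong to this study. This affects both the chance of a false pause at the historical rates and the chance of detecting excess risk. Second, a rule described as continuous has no table entry at sample sizes the trial will pass through. Seven deaths among 38, 39 or 40 evaluable patients meets the stated 90% criterion, but a reader working from the table would find nothing to trigger a review.

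**Working it through.** **Inputs, all from section 10.5 unless noted**

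- Historical rate p0: 0.10 (mortality), 0.15 (aGVHD).
- Prior with effective sample size 1 and mean p0: Beta(0.10, 0.90) and Beta(0.15, 0.85).
- Pause when Pr(p > p0 | data) > 0.90, checked after every evaluable patient from the second.
- Maximum number of patients: 37 (section 10.5) or 55 (sections 3.2 and 10.2.1).

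**1. Boundaries**

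After x events in n evaluable patients the posterior is Beta(p0 + x, 1 − p0 + n − x). The boundary b(n) is the smallest x for which Pr(p > p0) exceeds 0.90. It depends on n only, not on the maximum.

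This reproduces every printed cell of both tables from n = 2 to 54. At the edges of the gaps it gives:

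| Endpoint | n | x | Posterior | Pr(p > p0) | Boundary by the rule | Printed |
|---|---|---|---|---|---|---|
| Mortality | 38 | 7 | Beta(7.1, 31.9) | 0.927 | 7+ | none |
| Mortality | 39 | 7 | Beta(7.1, 32.9) | 0.918 | 7+ | none |
| Mortality | 40 | 7 | Beta(7.1, 33.9) | 0.908 | 7+ | none |
| Mortality | 41 | 7 | Beta(7.1, 34.9) | 0.898 | 8+ | 8+ |
| Mortality | 55 | 9 | Beta(9.1, 46.9) | 0.912 | 9+ | none |
| aGVHD | 38 | 9 | Beta(9.15, 29.85) | 0.905 | 9+ | none |
| aGVHD | 55 | 13 | Beta(13.15, 42.85) | 0.945 | 13+ | none |

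The missing cells at 38–40 and 38 continue the preceding row. At 55 the mortality boundary stays at 9+, while the aGVHD boundary steps up to 13+.

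**2. Crossing probabilities**

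Let a(n, x) be the probability of x events after n evaluable patients with no crossing so far. For a true rate p,

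a(n, x) = (1 − p)·a(n − 1, x) + p·a(n − 1, x − 1).

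At each n from 2 to the maximum, the mass with x ≥ b(n) is removed and added to the crossing probability. The calculation is exact. Results in %:

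| True rate | 5% | 10% | 15% | 20% | 25% | 30% |
|---|---|---|---|---|---|---|
| Mortality, stated | 4.8 | 24 | 53 | 78 | 92 | 98 |
| Mortality, maximum 37 | 4.9 | 24.0 | 53.3 | 78.4 | 92.4 | 97.9 |
| Mortality, maximum 55 | 5.0 | 27.4 | 63.3 | 88.4 | 97.6 | 99.7 |
| 55 minus stated | 0.2 | 3.4 | 10.3 | 10.4 | 5.6 | 1.7 |
| aGVHD, stated | 1.9 | 9.8 | 28 | 53 | 76 | 90 |
| aGVHD, maximum 37 | 1.9 | 9.8 | 27.5 | 52.6 | 75.7 | 90.3 |
| aGVHD, maximum 55 | 1.9 | 10.1 | 30.8 | 60.9 | 85.0 | 96.1 |
| 55 minus stated | 0.0 | 0.3 | 2.8 | 7.9 | 9.0 | 6.1 |

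All twelve stated values agree with a maximum of 37 to within 0.5 points, so that is the design the table describes.

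**3. Sensitivity**

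- With the printed boundaries and no look at the missing sizes, a 55-patient study gives mortality 5.0, 26.8, 62.0, 87.5, 97.3 and 99.6%, and aGVHD 1.9, 10.1, 30.7, 60.7, 84.9 and 96.1%. The largest difference from the stated values is then 87.5 − 78 = 9.5 points.
- If losses left only 50 of the 55 evaluable, the full mortality boundary would still give 60.6% at a true rate of 15% and 85.9% at 20%, against 53% and 78% stated.

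**The case against.** The stated probabilities are correctly calculated for the 37 patients named in the same section; they are out of date rather than miscalculated. The largest differences go in the reassuring direction, since the 55-patient rule detects excess mortality more often than printed. The unfavourable change, in false pauses at the historical rates, is about 3 points, and below those rates it is close to zero. All of this stands, but it does not rescue a table presented as describing the whole study.

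On the gaps, the 90% criterion is also stated in words and applies at any n, and a careful reader could carry 7+ and 9+ forward. Skipping every missing look lowers mortality crossing by at most 1.3 points (63.3 to 62.0% at a true rate of 15%) and aGVHD crossing by at most 0.2 points. The missing entry at 55 matters least: enrolment is complete by then, and it adds under 1 point for mortality and nothing for aGVHD. These points limit the practical effect. They do not make it acceptable for a prespecified safety boundary to be left to the reader.

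Crossing leads to a pause and DSMC review rather than automatic termination, and the DSMC also reviews reports at least twice a year (section 11.4). That softens the consequence but leaves the error in place.

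One further point stands as a caveat. Section 10.5 counts a patient with an event as evaluable at once, but a survivor only after 100 days. Looks made in real time will therefore over-represent events, which the exact calculation ignores. The 55-patient figures are nominal in the same sense as the printed ones.

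**Conclusion.** The point holds and should be corrected. The rule's stated maximum (37) contradicts the enrolment (55). The crossing probabilities are those of a 37-patient study and understate crossing in a 55-patient one, by up to 10.4 points for mortality (true rate 20%) and 9.0 points for aGVHD (true rate 25%). The boundary is unspecified at 38–40 and 55 for mortality, and at 38 and 55 for aGVHD. Every boundary that is printed agrees with the stated prior and criterion.

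The figures assume the section 10.5 prior and 90% criterion, a look after each evaluable patient from the second, independent outcomes arriving in enrolment order, and all 55 patients becoming evaluable. The finding does not question the historical rates or the 90% threshold.

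**What to change.** In section 10.5:

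- Change the stated maximum from 37 to 55.
- Complete the boundary tables with the values the plan's own criterion gives. Mortality: 34–40, 7+; 41–48, 8+ (unchanged); 49–55, 9+. aGVHD: 34–38, 9+; 39–43, 44–49 and 50–54 unchanged; add 55, 13+.
- Replace the probability table with the 55-patient values at true rates of 5, 10, 15, 20, 25 and 30%: mortality 5.0, 27, 63, 88, 98 and 99.7%; aGVHD 1.9, 10, 31, 61, 85 and 96%.
- Add a sentence saying that these probabilities assume outcomes become known in enrolment order.

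The cost is an amendment to tables and wording. The criterion, prior, sample size and primary analysis are untouched. The only less favourable disclosure is the false-pause probability at the historical rate, which rises from 24 to 27% for mortality and from 28 to 31% for aGVHD.

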5.5 GVHD Assessment

Patients will be monitored for development of acute and chronic GVHD, per standard operating procedures at the MCW BMT Program, but at minimum on days +28 (+/-7), +56 (+/-7), +100 (+/-14), +180 (+14), +365 (+/-28) post-HCT. Diagnosis of acute GVHD may not necessitate biopsy confirmation in at least one involved organ but would be preferred. When more than one organ is involved, biopsy confirmation of all involved organs is recommended but not necessary. With liver-only GVHD, biopsy confirmation is strongly recommended. Acute GVHD will be assessed by consensus criteria (Appendix 2), and chronic GVHD diagnosis and grading will be according to NIH Criteria (please see Appendix 2).

Independent GVHD adjudication is mandated in the study. Acute and chronic GVHD will be adjudicated by an independent Faculty Research Committee (FRC)-appointed review panel. Protocol PIs will be blinded to the adjudication panel and will not be permitted to grade or modify GVHD assessments. GVHD case report forms (CRFs) will be completed by treating MDs/NPs/APPs in real time, as indicated in study calendar. FRC adjudication panel will grade GVHD, using a calendar-driven approach (days +100 and +180 for aGVHD and days +180 and +365 for chronic GvHD).

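### The stopping rule counts events at once but event-free patients only at day 100, so its printed false-pause probabilities (24% and 28%) are too low

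*Combined protocol and SAP*

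**What the plan says.** Section 10.5 (Stopping Rules) sets a Bayesian boundary that "pauses the trial if we are 90% confident that the probability of the monitored event exceeds the historical value", with historical values of 10% for 100-day mortality and 15% for 100-day grade 3–4 aGVHD. The prior is "A Beta prior distribution with effective sample size of 1 and mean equal to the historical value". The boundaries were derived "with a maximum of 37 patients, and a continuous evaluation starting at two patients", and they are indexed by the number of evaluable patients. Evaluable patients are those who are "alive with at least 100 days of follow-up or have experienced the monitored event within 100 days are considered evaluable".

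A table then gives the probability of crossing for true rates of 5% to 30%. At the historical rates it prints 24% (mortality at 10%) and 28% (aGVHD at 15%). The text does not mention any allowance for pending patients.

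Section 5.5 (GVHD Assessment) describes two sources of aGVHD grade. Case report forms "will be completed by treating MDs/NPs/APPs in real time", and "FRC adjudication panel will grade GVHD, using a calendar-driven approach", which for aGVHD means days +100 and +180. Section 10.5 does not say which source feeds the rule.

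**The concern.** The evaluability sentence treats the two outcomes differently in time. At any look before follow-up is complete, recent patients who have had the event are in both numerator and denominator, while recent event-free patients are in neither. The observed proportion is biased upwards at every such look.

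For the aGVHD rule there is a second, permanent effect. A patient who dies before day 100 without grade 3–4 aGVHD is neither alive at day 100 nor an event, so is never counted.

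The DSMC and IRB have only the crossing table to tell them how often the trial would pause when nothing is wrong. If the table describes a different counting rule, that judgement rests on the wrong figure.

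**Working it through.** **Inputs from the documents.** Priors are Beta(0.1, 0.9) for mortality and Beta(0.15, 0.85) for aGVHD, with posterior threshold 0.90, looks from n = 2 and a maximum of 37 (section 10.5). Section 10.2.2 gives 50 transplants per year and "Assuming a conservative 40% enrollment rate", so accrual is 50 × 0.40 = 20 per year. On average 20 × 100/365.25 ≈ 5.5 patients are then inside their first 100 days.

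**Assumptions not in the documents.** Event day within the 100 days: 100 × Beta(1.5, 4) (early), uniform, or 100 × Beta(4, 2) (late). Deaths before day 100 without grade 3–4 aGVHD: 0% or 5%.

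**Step 1: boundaries.** With x events in n evaluable patients, cross if P(p > p0) > 0.90, where p ~ Beta(p0 + x, 1 − p0 + n − x). For mortality, 2 of 6 gives 0.904 (cross) and 2 of 7 gives 0.872 (do not cross). This matches the printed change from 2+ at 2–6 patients to 3+ at 7–12. The other printed limits also reproduce.

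**Step 2: the plan's own table.** Exact recursion, one fully observed patient at a time, N = 37:

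| True rate | Mortality, computed | Printed | aGVHD, computed | Printed |
|---|---|---|---|---|
| 5% | 4.9% | 4.8% | 1.9% | 1.9% |
| 10% | 24.0% | 24% | 9.8% | 9.8% |
| 15% | 53.3% | 53% | 27.5% | 28% |
| 20% | 78.4% | 78% | 52.6% | 53% |
| 25% | 92.4% | 92% | 75.7% | 76% |
| 30% | 97.9% | 98% | 90.3% | 90% |

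The printed table therefore assumes complete outcomes in sequence.

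**Step 3: an example of the difference.** Let patients enter every 365.25/20 = 18.3 days, and let patients 1 and 7 be the only deaths, patient 7 on post-transplant day 20. That is study day 6 × 18.26 + 20 ≈ 130. Patient 2 reached day 100 on study day 118; patient 3 will do so on day 137. The evaluable patients are 1, 2 and 7: two deaths in three, posterior 0.979, so the trial pauses. Counted in full and in order, two deaths in seven gives 0.872, and there is no pause.

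**Step 4: the rule as written.** 20,000 simulated trials per cell, Poisson entry at 20 per year, N = 37, patients ordered by event date or day 100:

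| Quantity | Early | Uniform | Late | Printed |
|---|---|---|---|---|
| Mortality, true 10% | 37% | 33% | 29% | 24% |
| aGVHD, true 15%, timing only | 45% | 40% | 36% | 28% |
| aGVHD, true 15%, 5% early deaths left out | 48% | 42% | 39% | 28% |
| aGVHD, true 15%, those deaths kept as non-events | 44% | 39% | 35% | 28% |

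Monte Carlo standard error is at most √(0.25/20,000) ≈ 0.4 points. At true mortality 5%, crossing is 7–10% against 4.8% printed.

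**Step 5: sensitivity.**
- aGVHD counted only at day 100 (adjudicated grade): 27–28%, or 30–31% with 5% early deaths left out.
- Accrual of 10 per year: mortality 27–30%, aGVHD 31–36%.
- With the staggered run-in of section 3.1: 28–36% and 34–43%.
- All events at day 99.9: back to 24% and 28%.

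The printed table's maximum of 37 against 55 enrolled is a separate matter and is not included above. On its own it moves the complete-outcome figures to 27.4% and 30.8%.

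**The case against.** The strongest objection concerns aGVHD. Section 5.5 mandates independent adjudication at day +100. If that grade drives the rule, the timing effect disappears and the printed 28% is about right, apart from the 2–3 points added by an assumed 5% of excluded deaths. This stands as a condition on the aGVHD figure. It does not touch mortality, which needs no adjudication.

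A second objection is look frequency. Section 11.4 has the DSMC reviewing reports twice a year. With six-monthly looks and uniform timing, crossing at N = 37 would be about 22% for mortality and 25–28% for aGVHD, near or below the printed values. But section 10.5 specifies continuous evaluation, and the printed table assumes it.

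Third, the excess sits at the start of the trial. With uniform timing, mortality crossings at six or fewer evaluable patients rise from 11% to 20%, which accounts for essentially all of the increase. The six run-in patients have already been treated, so the effect on the remaining trial is probably smaller; how many have reached day 100 is not stated.

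Finally, the error is cautious. A crossing leads to a pause and DSMC review, not automatic termination, and the GRFS test is unaffected. That limits the seriousness but does not make the printed figures correct.

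**Conclusion.** The concern holds. The crossing table describes a rule with complete, sequential outcomes, and section 10.5 defines a different one. For mortality at the historical 10%, the false-pause probability is about 29–37% rather than 24%, given continuous looks, 20 patients per year and events spread over the 100 days. For aGVHD at 15% it is about 36–45% if grades count in real time, or 39–48% with 5% early deaths excluded. It is 27–31% if the day +100 grade is used. The direction follows from the definition; the exact size depends on event timing, accrual and the early-death rate, which the documents do not fully give. The point should be corrected, but it threatens neither patient protection nor the primary analysis.

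**What to change.** 1. Amend the evaluability definition so that, for the aGVHD rule, a patient who dies before day 100 without grade 3–4 aGVHD counts as an evaluable non-event from the date of death.
2. State whether the real-time or the adjudicated aGVHD grade feeds the rule.
3. Keep the integer boundaries and the immediate counting of events, and recompute the crossing table by simulation under that counting rule at the planned accrual and enrolment, showing the range over event timing.

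The cost is two sentences and one re-run of the table. The stated false-pause probabilities become less favourable; change 3 reports the risk and does not reduce it. Change 1 slightly lowers aGVHD crossing when the true rate is raised. With 5% early deaths and N = 37, it falls from 64–71% to 59–68% at a true rate of 20%, and from 83–88% to 81–86% at 25%. Median time to pause changes by 4 days or less. Those deaths still count at once in the mortality rule.
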